## Protocol Synopsis

Title	A Randomized Multicenter Phase III Study of Individualized Stereotactic Body Radiation Therapy (SBRT) versus Trans-Arterial Chemoembolization (TACE) as a Bridge to Transplant in Hepatocellular Carcinoma.
Objective	
Primary:
 
 
• To compare the duration of disease control in treated lesions when utilizing SBRT versus TACE as a bridging strategy for patients with HCC eligible for liver transplantation.
 
 
Secondary:
 
 
• To determine health related quality of life (HRQL) for both treatment arms
 
• To compare toxicity
 
• To compare number of further interventions
 
• To compare pathologic response of treated lesion(s).
 
• To compare radiologic response of treated lesion(s).
 
• To assess 60 day Post-transplant morbidity and mortality
 

Study Design	A multicenter prospective randomized phase III trial
Sample Size	196 subjects will be enrolled
Eligibility	
Inclusion Criteria
 
 
1. Subjects with HCC are eligible for this trial. HCC is defined as having at least one of the following: 
 
• Biopsy proven HCC or:
 
• A discrete hepatic tumor(s) as defined by the Barcelona (29) criteria for cirrhotic subjects, <math>\geq 2</math>cm with arterial hyper vascularity and venous or delayed phase washout on CT or MRI.
 
 
 
2. Subjects are liver transplant candidates (actively awaiting organ transplant per transplant services in documentation), or, potential liver transplant candidates (at the discretion of the liver team and/or Principal Investigator) advised by liver transplant services as needing local treatment prior to liver transplant evaluation.
 
3. Subjects must be within UCSF criteria (one solitary tumor smaller than 6.5 cm, or patients having 3 or fewer nodules, with the largest lesion being smaller than 4.5 cm or having a total tumor diameter less than 8.5 cm without vascular invasion) and eligible for potential liver transplant.
 
4. Subjects must be eligible for TACE and SBRT procedures.
 
5. Subjects must have a life expectancy of at least 12 weeks.
 
6. Subjects must be 18 years of age or older. Adult subjects of all ages, both sexes and all races will be included in this study.
 
7. Subjects must sign an informed consent form approved for this purpose by the Institutional Review Board (IRB) of record.
 
8. Subjects must have a Child-Turcotte-Pugh (CTP) score <math>\leq 8</math>.
 
9. Patients must have adequate organ function within 2 weeks of enrollment.
 

	
 
• Bone marrow: Platelets <math>\geq 30,000/\text{mm}^3</math>
 
• Renal: BUN <math>\leq 40 \text{ mg/dl}</math>; creatinine <math>\leq 2.0 \text{ mg/dl}</math>
 
• Hepatic: INR <math>\leq 1.5</math> or correctable by Vitamin K, unless anti-coagulated for another medical reason
 
• Bilirubin <math>< 3.0 \text{ mg/dl}</math> (in the absence of obstruction or pre-existing disease of the biliary tract, e.g. primary sclerosing cholangitis).
 
 
10. Patients' uninvolving liver volume will be estimated and must be <math>> 700\text{ml}</math>.
 
11. Patients must have a Zubrod performance status of <math>\leq 2</math>.
 
12. Patients who are sexually active must agree to the use of contraception throughout the duration of the study.

	
Exclusion Criteria
 
 
1. Subjects in a “special category” as designated by FDA and the Canadian Institutes of Health or Canadian Panel on Research Ethics , Including subjects younger than 18, pregnant women, and prisoners.
 
2. Refractory ascites that requires paracentesis for management.
 
3. Known allergy to intravenous iodinated contrast agents unresponsive to prednisone pre-treatment.
 
4. History of prior radiation to the liver.
 
5. Evidence of metastatic disease.
 
6. Presence of a Trans-jugular intra-hepatic porto-systemic shunt (TIPS).
 
7. Untreated varices at high risk of bleeding
 
8. Bile duct occlusion or a prior diagnosis of an incompetent papilla
 
9. Acute infection.
 
10. Uncorrectable bleeding disorder.
 
11. leukopenia, ANC <math>< 1000/\text{ul}</math>
 
12. hepatic encephalopathy
 
13. portal vein thrombosis
 

Intervention	Stereotactic Body Radiation Therapy (SBRT) versus Trans-Arterial Chemoembolization (TACE)
Assessments	Physician Exam, Abdominal MRI or CT, Chest CT or X-ray, MELD-Na, ALBI score, CTP score, Labs, HRQL

## A. ABSTRACT

For patients with hepatocellular carcinoma (HCC) awaiting liver transplantation, local regional treatment of their disease has become the standard of care in an effort to decrease dropout rates and as a means of reducing tumor recurrence after transplantation (1). Retrospective single institution data suggests a survival benefit for patients undergoing bridging therapy prior to liver transplantation and a recent meta-analysis noted a non-significant trend toward reduced waitlist dropout and improved post-transplant outcomes, while acknowledging the absence of prospective randomized data (2). Additionally, there is no standard of care regarding appropriate bridging strategies, although TACE is the most commonly performed bridging procedure in The United States (3). Recently, newer bridging modalities other than TACE have shown similar rates of local regional control for patients with unresectable HCC. One such treatment modality is SBRT. SBRT has been shown to afford good local control and acceptable safety when utilized in patients with HCC. We propose to conduct a multi-center prospective randomized Phase III trial to compare SBRT to TACE as a bridging strategy for patients with HCC undergoing liver transplantation.

## B. SPECIFIC AIMS

**Hypothesis:** SBRT will be associated with longer time intervals between initial treatment and the need for retreatment, compared to TACE, when used as a “bridge” to liver transplantation in subjects with HCC.

### 1.0 Primary endpoint:

Time from randomization to date of progression or residual disease of previously treated lesions as determined by the date of the radiologic imaging.

### 2.0 Secondary endpoints:

- Health related quality of life (HRQL) for both treatment arms
- Toxicity
- Number of further interventions
- Pathologic response of treated lesion(s)
- Radiologic response of treated lesion(s)
- 60 day Post-transplant morbidity and mortality

## C. BACKGROUND AND SIGNIFICANCE

HCC is the sixth most common cancer with an increasing incidence worldwide, and is the third leading cause of cancer-related death (4-5). Given that people who develop HCC typically have concomitant cirrhosis, the best opportunity for cure for most patients is liver transplantation. Because organ donors are scarce, patients who are eligible for liver transplantation may wait many months before receiving a liver. Recently, local regional interventions have been utilized as a temporizing strategy to "bridge" individuals with HCC who are awaiting transplantation. The aims of bridging treatments include: decreasing the waiting list dropout rate for transplantation due to HCC progression beyond acceptable criteria; reducing recurrent HCC after transplantation; and improving post-transplant overall survival (6). For patients undergoing local regional therapy as a bridge to transplantation, TACE is the most commonly utilized treatment (7).

TACE is a therapy that combines the local delivery of chemotherapy with the induction of tumor ischemia through obstruction of the feeding vessels. Two randomized controlled trials (RCTs), conducted in Europe and Asia, showed an increased survival for subjects treated by embolization with an emulsion of a chemotherapy agent and iodized oil when compared to conservative treatment. Llovet et al. reported 1-year and 2-year survival of 82% and 63%, respectively. Lo et al. found significant improvement in survival for Asian HCC subjects treated by chemoembolization (8,9). Drug-Eluting Beads (DEB) such as Quadraspheres® (of which there are several on the market) are an agent for chemoembolization with the ability to load doxorubicin. In vitro data has shown a slow release of doxorubicin over time with a decreased systemic blood serum levels and increased tumor tissue levels of the chemotherapeutic agent (10-13).

Several pilot studies have evaluated the safety and efficacy of DEB-TACE. Poon et al showed good tumor response and limited toxicity in subjects with incurable HCC and Child-Pugh class A cirrhosis. No dose-limiting toxicity was observed for up to 150 mg doxorubicin. The pharmacokinetic study showed a low peak plasma doxorubicin concentration and no systemic toxicity was observed. The treatment-related complication rate was 11.4%. There was no treatment-related death. Among 30 subjects who completed 2 courses of DEB-TACE, the partial response rate and the complete response rates were 50 and 0%, respectively, by response evaluation criteria in solid tumors (RECIST) criteria at computerized tomography scan 1 month after the second DEB-TACE. By modified RECIST criteria, taking into account the extent of tumor necrosis, 19 (63.3%) subjects had a partial response and 2 (6.7%) had a complete response (14). Varela et al evaluated the safety, pharmacokinetics and efficacy of TACE using drug eluting beads. DEB-TACE was well tolerated with an acceptable safety profile. Two cases developed liver abscess, one leading to death. Response rate was 75% (66.6% on intention-to-treat). Doxorubicin Cmax and AUC were significantly lower in DEB-TACE subjects than in conventional TACE. After a median follow-up of 27.6 months, 1- and 2-year survival is 92.5 and 88.9%, respectively (15).

Malagari et al conducted an open-label, single-center, single-arm study of DEB-TACE in 62 cirrhotic subjects with documented solitary unresectable HCCs. Mean tumor diameter was 5.6 cm (range, 3-9 cm) classified as Okuda stages 1 (n=53) and 2 (n=9). Subjects received repeat embolizations with doxorubicin-loaded beads every 3 months (maximum of three treatments). The maximum doxorubicin dose was 150 mg per embolization, loaded in DC Beads® of 100-300 or 300-500  $\mu$ m. Post-treatment, an objective response according to the European Association for the Study of the Liver (EASL) criteria was observed in 59.6%, 81.8%, and 70.8% across three treatments. At 9 months a complete response was seen in 12.2% of subjects. Severe procedure-related complications were seen in 3.2% (cholecystitis, n=1; liver abscess, n=1). Post-embolization syndrome was observed in all subjects (16). Several studies have since shown that DEB-TACE not only is favorable compared to conventional TACE regarding side effects but may elicit a better overall outcome. Song demonstrated in the Asian population a better treatment response and delayed tumor progression with DEB-TACE (17).

In a multicenter study including 201 European subjects (PRECISION V), use of DC Beads® resulted in a clinically and statistically significant reduction in liver toxicity and drug-related adverse events compared with conventional TACE with lipiodol and doxorubicin (18, 19). Two other trials reported higher rates of tumor response and longer time to progression for the loaded DC Bead as compared to a bland embolic microsphere with similar characteristics (20, 21). As a result of these investigations, DEB-TACE has been increasingly used as therapy for bridging treatment in subjects awaiting transplantation with HCC, although embolic beads without chemotherapy are also widely used (22).

Despite its increased utilization, DEB-TACE (or any strategy) as a bridge to liver transplantation remains of uncertain benefit. To date, multiple retrospective analyses suggest a benefit of pre-operative treatment for subjects with HCC awaiting liver transplantation, but no data from prospective randomized trials are available establishing DEB-TACE as an effective strategy to reduce the risk of recurrent HCC following transplantation or to improve survival (22). Furthermore, there is conflicting data regarding whether TACE should be performed with chemotherapy or as a “bland” particle and whether one or more procedures ought to be performed. Additionally, there has been no attempt to compare TACE, radiofrequency ablation (RFA), resection, or other treatment strategies utilized to bridge subjects to liver transplantation. In the absence of a standardized approach, there is no definitive standard-of-care either *within a given treatment strategy or between different treatment approaches* and hence, different preoperative treatments using varied protocols are employed by different institutions for different individual subjects awaiting transplant.

A newer strategy for the treatment of HCC is SBRT. Historically, external beam radiation lacked adequate precision and was considered too toxic to be utilized to ablate tumors within the liver. With large volume irradiation, the risk of radiation-induced liver disease (RILD) is prohibitive (23-27). However, over the past two decades, advances in computer and imaging technologies have improved conformal radiation such that it has become a feasible and safe technique for focal treatment to the liver with RILD rates of less than 10% in early stage patients. SBRT uses a small number of high dose fractions of highly conformal radiation therapy, delivered with high geometric precision and accuracy. SBRT offers some theoretical advantages compared to other local regional strategies for the treatment of HCC. First, a uniform dose of radiation is delivered to the entire tumor. There is no necessity of uniform blood flow which can be an issue with treatments such as TACE directed through liver vasculature. Second, no direct manipulation of the primary tumor is necessary. Hence, any concerns for HCC spread through needle tract dissemination such as can occur in radiofrequency ablation or other percutaneous interventions are absent. Third, given that no direct manipulation of hepatic vasculature is necessary, potential damage to vascular structures is of no concern. Fourth, it may be more cost effective than other treatment strategies as there is no requirement for hospitalization in comparison with subjects undergoing TACE.

Retrospective studies and two prospective studies suggest that SBRT to the liver can be used safely for the treatment of metastatic cancer with local control rates of 75% to 100% at 1 to 2 years (28). Data from Bujold et.al., utilizing SBRT for locally HCC, showed good effect and acceptable toxicity when compared to historical data regarding TACE or other equivalent strategies. The one year tumor control rate was 87% (29). A retrospective comparison by Sapir et.al. compared HCC patients with similar disease burdens treated with either SBRT or TACE and found SBRT to be safe for 1 to 2 tumors while providing better local control (30). Furthermore, a recent comparison of SBRT to TACE or RFA by Sapisochin et.al. found that SBRT can be safely utilized as a bridge to transplant in HCC patients as an alternative to conventional bridging strategies (31).

Given these potential advantages, in September 2014 Lahey Hospital and Medical Center initiated a randomized feasibility trial prospectively comparing SBRT to DEB-TACE in the treatment of HCC as a bridge to liver transplantation. With an expected enrollment of 60 patients, we have presently enrolled 45 patients with 31 eligible for evaluation. These data were presented as an Oral Abstract at the American Society of Clinical Oncology Gastrointestinal Cancer Symposium in January 2017. While preliminary, our data indicate that SBRT appears at least as effective as DEB-TACE at controlling tumors prior to transplant, may engender less toxicity, may better preserve quality of life, and may cost less (32-33).

In the current study, we propose to compare individualized SBRT to TACE as a bridge to liver transplantation in patients with HCC.

## **D. RESEARCH DESIGN AND METHODS**

### **1.0 Eligibility**

#### **1.1 Inclusion Criteria**

- Subjects with HCC are eligible for this trial. HCC is defined as having at least one of the following:
  - Biopsy proven HCC or:
  - A discrete hepatic tumor(s) as defined by the Barcelona (29) criteria for cirrhotic subjects,  $\geq$  2cm with arterial hypervascularity and venous or delayed phase washout on CT or MRI.
- Subjects are liver transplant candidates (actively awaiting organ transplant per transplant services in documentation), or, potential liver transplant candidates (at the discretion of the liver team and/or Principal Investigator) advised by liver transplant services as needing local treatment prior to liver transplant evaluation.
- Subjects must be within UCSF criteria (one solitary tumor smaller than 6.5 cm, or patients having 3 or fewer nodules, with the largest lesion being smaller than 4.5 cm or having a total tumor diameter less than 8.5 cm without vascular invasion) and eligible for potential liver transplant.
- Subjects must be eligible for standard TACE and SBRT procedures.
- Subjects must have a life expectancy of at least 12 weeks.
- Subjects must be 18 years of age or older. Adult subjects of all ages, both sexes and all races will be included in this study.
- Subjects must sign an informed consent form approved for this purpose by the Institutional Review Board (IRB) of record.
- Subjects must have a Child-Turcotte-Pugh (CTP) score  $\leq 8$ .
- Patients must have adequate organ function within 2 weeks of enrollment.
  - Bone marrow: Platelets  $\geq 30,000/\text{mm}^3$
  - Renal: BUN  $\leq 40 \text{ mg/dl}$ ; creatinine  $\leq 2.0 \text{ mg/dl}$
  - Hepatic: INR  $\leq 1.5$  or correctable by Vitamin K, unless anti-coagulated for another medical reason
  - Bilirubin  $< 3.0 \text{ mg/dl}$  (in the absence of obstruction or pre-existing disease of the biliary tract, e.g. primary sclerosing cholangitis).
- Patients' uninvolved liver volume will be estimated and must be  $> 700\text{ml}$ .
- Patients must have a Zubrod performance status of  $\leq 2$ .
- Patients who are sexually active must agree to the use of contraception throughout the duration of the study.

#### **1.2 Exclusion Criteria**

- Subjects in a “special category” designated by the Public Health Service, Including subjects younger than 18, pregnant women, and prisoners.

- Refractory ascites that requires paracentesis for management.
- Known allergy to intravenous iodinated contrast agents unresponsive to prednisone pre-treatment.
- History of prior radiation to the liver.
- Evidence of metastatic disease.
- Presence of a Trans-jugular intra-hepatic porto-systemic shunt (TIPS).
- Untreated varices at high risk of bleeding
- Bile duct occlusion or a prior diagnosis of an incompetent papilla
- Acute infection.
- Uncorrectable bleeding disorder.
- leukopenia, ANC <1000/uL
- hepatic encephalopathy
- portal vein thrombosis

## 2.0 Pretreatment Evaluation

Subjects will be consented for the study prior to starting treatment.

2.1 Subjects will undergo a comprehensive liver evaluation per the treating physician's discretion, including a complete history of viral status (Hep. C, Hep. B or No) and physical examination, baseline assessments of organ function and documentation of measurable disease (contrast-enhanced CT or MRI) parameters chest CT or Chest X-ray), weight, and health related Quality of Life measures.

2.2 Laboratory evaluation.

2.3 Assessment of clinical measures of severity of liver disease: The Model for End-Stage Liver Disease (30) (MELD-Na) and the CTP classification are models used for the clinical assessment of subjects with liver dysfunction (Appendix A). Subjects with CTP classification Grade A versus Grade B appear to have increased sensitivity to radiation. Additionally, in a study of subjects treated with SBRT for HCC or intrahepatic cholangiocarcinoma, 17% experienced progression from CTP Grade A to Grade B within 3 months after radiation therapy (31, 32), suggesting that CTP may be a useful assessment of worsening liver function. MELD may perform even better than CTP at evaluating liver function (33). We propose to record these clinical measures (MELD-Na and CTP, and Albumin-Bilirubin (ALBI) score, and assess their potential contribution to individualize our assessment of liver injury that could be used to adjust liver dose.

2.4 Assessment can be performed by any medical provider in the liver transplant team including hepatology/gastroenterology, medical oncology, radiation oncology, interventional radiology and transplant surgery or as medically necessary per standard treatment

## 3.0 Randomization Plan

All consented subjects will receive a Study Identification Number (SID) in the EDC system. The SID number will be a 4 digit number. The first two digits are site number. Site number will be assigned by the Coordinating Center at Lahey and it will start with 01 with 1 increment for each site (that is 01, 02, 03, etc.). The last two digits are the patient screening order starting from 01. Eligible subjects will be randomized after eligibility is confirmed by the provider, as soon as practical to the baseline tumor scan. Randomization will be performed using randomly selected block sizes of 2, 4 and 6 and stratified by the

following factors identified at screening: CTP score (either A or B) and disease etiology (with or without Hepatitis C). The randomization ID will be a 5 digit number in the form of ABCDE where, AB denote the site number, C indexes the four strata used for the randomization and DE index the order of screening at that site. C will be one of the numbers from 1 to 4. DE is the patient screening order starting from 01. Each study site will receive randomization list from the Coordinating Center at Lahey and randomize the eligible subjects individually. Site staff involved in randomizing subjects will not be aware of the randomization sequence before randomization. Randomization will be documented on both source document and EDC indicating assignment. If a patient is lost from the study because they are unable to receive their randomized treatment then an additional patient will be enrolled.(i.e., unable to meet SBRT dose constraints or achieve an acceptable respiratory motion strategy for SBRT). Individual randomization codes will be not be reused.

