## 15.0 Statistical Considerations

This is a randomized, non-blinded, Phase III trial to characterize the safety and efficacy of individualized SBRT, compared to TACE, for subjects who have primary HCC. The trial endpoints are time to progression or residual disease in the treated lesion(s), number of retreatments, radiologic response, pathologic response, toxicity, and HRQL, overall survival, and 60 day post-transplant morbidity and mortality.

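### Section 3.0 sends the randomization list to the sites that randomize, in a non-blinded trial, and gives no mechanism to back its statement that the sequence is concealed.

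*Combined protocol and SAP*

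**What the plan says.** Section 3.0 places both the list and the act of randomizing at the site: "Each study site will receive randomization list from the Coordinating Center at Lahey and randomize the eligible subjects individually". The next sentence is the only statement on concealment: "Site staff involved in randomizing subjects will not be aware of the randomization sequence before randomization".

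The same section discloses the blocking: "Randomization will be performed using randomly selected block sizes of 2, 4 and 6". It names two stratification factors, Child-Turcotte-Pugh class and hepatitis C status. Site is not named as a factor. The randomization ID does begin with the site number, and then "C indexes the four strata used for the randomization and DE index the order of screening at that site".

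The EDC system has two roles in section 3.0: it issues the study identification number, and it is one of the two places where the assignment is recorded. It is not described as releasing assignments. Section 15.0 confirms that treatment is open: "This is a randomized, non-blinded, Phase III trial".

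**The concern.** Randomization protects the comparison only if whoever decides on entry cannot foresee the next arm. Here the list is with the party that enrolls, and the safeguard is a sentence without a procedure. Several features of this trial would give foreknowledge something to act on:

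- **Entry involves judgement.** Section 1.1 admits potential transplant candidates at the discretion of the liver team or investigator, and requires each subject to be fit for both procedures.
- **The assessors may deliver the treatments.** Section 2.4 lets any transplant-team provider do the pretreatment assessment, including radiation oncology and interventional radiology.
- **Timing is loose.** Section 3.0 asks for randomization as soon as practical relative to the baseline scan, and Tables 2 and 3 accept an abdominal scan from 4-6 weeks before enrollment. A patient could be held back.
- **The endpoint is read locally.** Under section 11.2 the treating institution reads the images, and the central panel sees them only when two local readings disagree. Sound allocation is therefore one of the main protections left.

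If patients were steered toward or away from an arm, the analysis could not reliably undo it, because the judgements behind the steering are not fully recorded.

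**Working it through.** The plan states no figure for predictability, so there is none to reproduce. The check has two parts.

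**1. Is there a mechanism?** Set the two sentences of section 3.0 side by side. The site receives the list and randomizes from it; the randomizing staff do not know the sequence. Both can be true only if something stands between the list and those staff, such as sequential sealed envelopes, a list holder with no part in enrollment, or central release. None of these appears anywhere in the document. The assurance also reaches only staff involved in randomizing. Section 3.0 makes confirmation of eligibility a separate step done by the provider, who is not covered.

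**2. How far can the next arm be guessed from past assignments alone?**

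Inputs from the documents: block sizes 2, 4 and 6; 1:1 allocation (98 per arm, Table 7); four strata; 196 subjects (synopsis), hence 196/4 = 49 per stratum on average; no blinding.

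Assumptions: the three block sizes are equally likely (probabilities are not given), and the guesser names the arm that is behind in the assignments he or she can see, or tosses a coin if they are level.

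*Second patient in a list.* In a block of size b, the second assignment is the opposite of the first with probability (b/2)/(b-1). This is 1, 2/3 and 3/5 for b = 2, 4 and 6. The average is (1 + 0.667 + 0.600)/3 = 0.756. That is the most favorable early position and does not represent the whole list.

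*Whole list, separate lists per site and stratum.* Permuted blocks were simulated, with all earlier assignments in the list visible. The share certain is the share of assignments fully determined for someone who knows the possible block sizes.

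| Patients in list | Correct guess, 2/4/6 | Correct guess, 4/6 | Certain, 2/4/6 | Certain, 4/6 |
|---|---|---|---|---|
| 4 | 0.666 | 0.655 | 0.9% | 1.3% |
| 6 | 0.686 | 0.672 | 2.8% | 7.0% |
| 10 | 0.689 | 0.681 | 3.3% | 5.9% |
| 49 | 0.697 | 0.688 | 4.0% | 5.6% |
| 196 | 0.702 | 0.693 | 4.1% | 5.5% |

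The guess is therefore right about 67-70% of the time under the planned blocks, against 50% with no information.

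*Blocks shared across sites.* Section 3.0 does not name site as a factor, so this reading is open. The simulation used 49 patients in a stratum spread at random over the sites, each site seeing only its own past assignments. The number of sites is not given, so a range was run. The correct-guess rate is about 52% with 5 sites and about 51% with 10 or 15.

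The range over the two readings is thus about 51% to 70%, and it depends mainly on a point the plan leaves unstated.

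**The case against.** The strongest reply is that the plan does assert concealment, in the sentence right after the one about the list. A list sent to a site need not be readable by the people who randomize; it may be in sealed form or held by someone outside enrollment. Section 18.0 refers to a detailed operations manual covering all implementation tasks at the sites, and the mechanism may be there. This stands in part. A reader might infer that upcoming assignments are known to the sites, so that every one is predictable. The documents do not support that: it presumes a readable list, and the plan says randomizing staff do not see the sequence. The reply does not dispose of the point, because the safeguard is not described where the procedure is set out and does not cover the provider confirming eligibility.

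A second reply is that block sizes vary at random, which is a recognized protection, and that a guess rate near 70% is a modest edge common to stratified blocking in open-label trials. That is fair. Few assignments are certain (about 1-4%), and if blocks run across sites almost no edge remains.

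A third is that randomization follows confirmed eligibility and every subject must suit both procedures. This limits steering, but leaves the judgement and timing of the eligibility decision itself.

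A reader might also infer that the block of size 2 is the culprit and should go. The figures say otherwise. Dropping it lowers the guess rate by about one percentage point (0.689 to 0.681 at 10 patients, 0.702 to 0.693 in long lists) and raises the share of certain assignments (3.3% to 5.9%, and 4.1% to 5.5%).

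**Conclusion.** The point holds as a weakness in the stated procedure, with a better and inexpensive alternative. The protocol gives the list to the party that enrolls, in a trial where treatment is open and the block sizes are published, and supports concealment with an assurance that has no mechanism and does not cover the eligibility decision. No breach of concealment is shown.

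The size of the residual guessing problem is conditional. It is about 67-70% correct if lists are separate by site and stratum, which the per-site lists and the ID format suggest but do not state. It is about 51-52% if blocks are shared across sites, assuming 49 patients per stratum and 5-15 sites. Both figures assume equally likely block sizes. The main weakness is where the list is held; the choice of block sizes matters little. This should be corrected, but by itself it does not invalidate the design.

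**What to change.** Revise section 3.0 in four respects:

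- Do not send lists to sites. Hold the list at the coordinating center, under someone with no part in enrollment.
- Release one assignment at a time through the EDC system already in use, only after eligibility has been confirmed and locked and the stratum entered.
- State whether lists are separate by site, and extend the concealment statement to everyone who confirms eligibility.
- Move the block sizes to a randomization document that the sites do not see. The sizes themselves can stay.

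If a concealment procedure already exists in the operations manual, describe it in section 3.0, and still prefer central release.

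The cost is EDC set-up and testing. The 196 subjects and 120 events do not change.
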